### 5.3 JUSTIFICATION FOR INTERVENTION

Intervention delivery via mobile software app is precisely central to the potential benefit of the intervention: in-the-moment support for patients' capacity to interact with complex written patient materials. We will only have two actual study contacts beyond recruitment and pre-screen/consenting: baseline and follow-up at three months, which will only include obtaining outcome measurement administration necessary to analyze data to meet our study objectives. We will have app usage data (internal to GogyUp) that can provide any indication as to whether lack of differences between arms in an intent-to-treat analysis is simply due to low app usage (this would provide a finding, and inform future study design, rather than being a failure).

### 5.4 END-OF-STUDY DEFINITION

Participants will be considered to have completed the study if they have completed the baseline and three-month follow-up assessments.

The end of the study is defined as completion of the 3-month follow-up assessment shown in the Schedule of Activities (SoA), **Section 2.3.**]

## 6 STUDY POPULATION

### 6.1 INCLUSION CRITERIA

In order to be eligible to participate in this study, an individual must meet all of the following criteria:

1. Provision of signed and dated informed consent form
2. Males and females; Aged 18-85 years
3. Documented diagnosis of type II diabetes mellitus
4. Has had a visit to an MHealth Fairview clinic in the past year (November 2021- November 2022); can include a telehealth visit

### 6.2 EXCLUSION CRITERIA

An individual who meets any of the following criteria will be excluded from participation in this study:

1. Currently enrolled in another treatment or intervention study (at pre-screen)
2. Pregnancy (because pregnancy becomes the primary condition of interest in treatment)
3. Blind

Note: Although it is assumed that most participants placed in the GogyUp Reader group will have access to necessary resources for participating in a technology-based intervention (i.e., computer, smartphone, internet access) such access will NOT be a criterion - GogyUp will make a limited supply of hardware and data plans available to participants without consistent, reliable internet access.

### 6.3 LIFESTYLE CONSIDERATIONS

During this study, participants are not asked to maintain any additional lifestyle alterations or considerations.

### 6.4 SCREEN FAILURES

Screen failures are defined as participants who consent to participate in this study but are not subsequently assigned to the study intervention or entered in the study. Individuals who do not meet the criteria for participation in this trial (screen failure) because of meeting one or more exclusion criteria will not be rescreened.

### 6.5 STRATEGIES FOR RECRUITMENT AND RETENTION

We plan on asking our clinical partner, MHealth Fairview, to sample 2,000 individuals, with the understanding that some may fail pre-screening, to reach our needed sample size (our maximum sample size with no screening failures would be 200). Given that our sampling frame is patients in a health system serving communities within the Twin Cities metro region, with a focus on clinics serving relatively high proportions of low-income/publicly insured patients, and given some non-response and pre-screen failures

might occur, we anticipate an enrollment sample size of 160 individuals, evenly divided by gender, with most participants 45 years old or older (possibly a median age of 55, with a possible range of the full 18-85 age range); with approximately 50 to 60 percent of our sample being White and non-Hispanic/Latino, 20 to 30 percent Black non-Hispanic, 10-15 percent Hispanic/Latino, and another 10-15 percent of other groups. We do plan to prioritize diversity of racial and ethnic groups in our sample in collaboration with our research/trial support partner at the point of sample identification and recruitment (prioritizing sample identification and recruitment contact to oversample Black, Indigenous, Hispanic/Latino, Asian and Pacific Islander, and multiracial ethno-racial categories).

Due to the ongoing COVID-19 pandemic, potential future waves of infection, and limited clinic capacity to accommodate studies, a clinic site-based recruiting approach is both inefficient and less likely to succeed within the study timeframe, would require additional considerations for participants' privacy and safety, and potentially limit the diversity of the available patient pool.

For recruitment, we have contracted with a local health system, M Health Fairview, to send out a letter mailer to patients meeting the inclusion and exclusion criteria noted in Section 5.1 and 5.2. The letter invites these patients to the study and to contact our research coordinators by call, email, or text or by visiting a website with a contact form. Upon initial contact by interested patients, GogyUp's research coordinators will perform [the remote consent / enrollment / placement workflow.](#)

Candidates who enroll and are placed in the intervention group will be asked to use their personal devices. If a participant placed in the intervention group does not have regular, consistent access to an Internet-connected device will be provided a cellular-enabled tablet with an active SIM card for the duration of their participation. Participants who use their own intent-connected devices will be sent a \$25 gift card at baseline to offset network expenses.

All participants, whether they are in the control group or are in the intervention group, will receive a \$25 gift card in compensation at the end of the study period. These measures will assist both with ensuring that the intervention is not hindered by technological or network access barriers and also provide both an incentive to stay enrolled, helping to ensure retention. We will also obtain multiple forms of contact information from consented participants to ensure we can contact them at follow-up. We believe our proximal outcome and short follow-up will further ensure retention and completion.

## 7 STUDY INTERVENTION(S) OR EXPERIMENTAL MANIPULATION(S)

### 7.1 STUDY INTERVENTION(S) OR EXPERIMENTAL MANIPULATION(S) ADMINISTRATION

#### 7.1.1 STUDY INTERVENTION OR EXPERIMENTAL MANIPULATION DESCRIPTION

The study intervention is the use of the GogyUp Reader app. The GogyUp Reader is a software app that can be used on mobile phones, tablets, and PCs. and is designed to

provide both in-the-moment support for interacting with written materials, combined with activities designed to address overall functional adult print literacy. This is intended to address personal capacity to deal with complex written patient education or care plan materials on an as-needed, low-cost/free and low-burden basis. This mechanism (in-the-moment support with written materials) is supported theoretically by Co-PI [name]'s theoretical model of patient complexity, the Cumulative Complexity Model, which posits that problems with patient access to care and self-care or adherence arise from an interaction between the work that patients are asked to do (in life and in caring for their conditions) and the capacity they have to do it. This model has been supported all or in part in both systematic reviews and intervention designs. In brief, complex patient written materials add burden to the workload of being a patient with diabetes— and without sufficient capacity, patients are not in a position to use those patient education or care plan materials in the way they need to— the definition of functional health literacy. While other interventions are designed to increase patients' capacity through either in-clinic sessions, additional materials or differently designed materials, or time-and resource-intensive coaching, the mechanism of action with GogyUp Reader as an intervention is that the support for capacity is available exactly when patients need it, allowing them to understand materials and successfully enact self-care. The control condition will consist of the written materials (and other clinical guidance) that patients normally receive (essentially a usual care arm), without GogyUp Reader.

---

### 7.1.2 ADMINISTRATION AND/OR DOSING

Given that this study involves assistive-reading technologies, administration and dosing are problematic concepts. However, to specify: participants will install GogyUp Reader app onto their devices (or devices supplied by GogyUp upon request) at baseline. A brief tutorial will be given by GogyUp staff trained in the protocol. The analog to “dosing” here is the degree to which participants might be expected to use the app or, if in the control group, review the paper documents. We are not requiring any particular level of app usage; our preliminary app usage data (GogyUp internal app data) have indicated consistent levels of self-directed app usage data in past applications and, to the degree intervention participants did not use the app, GogyUp would be able to see that in the app’s activity data (or lack thereof). Of course for the control group, activity data is not measurable.

## 7.2 FIDELITY

---

### 7.2.1 INTERVENTIONIST TRAINING AND TRACKING

The protocol objectives for this study do not depend on consistent administration of the study intervention beyond the baseline visit. To date, the GogyUp Reader app has been used for multiple sessions, and in some cases over months and years, by over 1,500 adult learners with minimal digital literacy and a wide range of print literacy and English proficiency. The majority of these adults installed the app on their own while a minority need brief training while enrolled an adult basic education setting. To ensure consistent onboarding and app usage, a standard script for downloading the app onto devices will

be used during a brief tutorial at the baseline visit to ensure standard initial introduction of the GogyUp Reader (study intervention). Technical support will also be provided by trained GogyUp personnel through email and a dedicated phone number capable of receiving voice calls and text messages.

### 7.3 MEASURES TO MINIMIZE BIAS: RANDOMIZATION AND BLINDING

We will use a random allocation sequence from the National Cancer Institute's Clinical Trial Randomization Tool (<https://ctrandomization.cancer.gov/tool/>). Study staff will refer to the allocation sequence to determine allocation arm for each newly recruited participant.. As such, study staff not involved in analysis will not be blinded because they will provide initial access to the GogyUp Reader app. Lastly, using an encrypted Microsoft Excel file for which only study staff not involved in analysis will have the password, study staff will create and enter the study id and trial arm into two crosswalk files: the first, a crosswalk identifying study id number with study arm (for unblinding following blinded analysis), and a crosswalk file linking intervention-arm study identification numbers to a separate id number from GogyUp internal data (for assessments of adherence; see above). Study staff will then enter name, contact information, study id and baseline variables into REDCap. Investigators (Drs. [name], [name], and [name] and [name]) will be blinded to participants' status, only have access to the REDCap file prior to analysis, and indeed will not have contact with participants. To support interim analysis, all procedures above will be followed, but for participants recruited during the first three months, an additional study id variable (interim study id) and REDCap trial arm indicator (interim indicator) will be used— these will ensure that the interim analysis (see above) does not effectively unblind the full analysis. After *interim* analysis, study staff will use the encrypted file to inform the investigators which random study arm number indicated which study arm. After *final* analyses, study staff will provide the password for the encrypted crosswalk files to the investigators for unblinding. The criterion for unblinding will be that all participants have had a final follow-up visit and (masked/blinded) comparative analyses are complete. In the unlikely event of an *unplanned* unblinding/breaking of randomization indicators, because investigators have no contact with participants and this protocol will be registered publicly, instigators will simply report the unplanned breaking and reasons for it in all subsequent publications for transparency.

As noted above, study staff cannot be blinded but staff and investigators will have no other contact with participants other than staff administration of follow-up questionnaires. Staff enrolling and administering baseline and follow-up assessments will not have a role in analysis and investigators will not have access to blinded materials until after analysis nor have contact with participants.

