# RCT of Assistive-Reading Technology for Post-Visit Type 2 Diabetes Patient Education

Version 1.4

Protocol 1

10 February 2023

Due to rolling recruitment, the full study is expected to take up to 12 months, although if recruitment is faster than expected, the overall study may take less time.

Randomization is detailed below. In brief, we will randomize participants 1:1 at the individual level at enrollment using pre-generated trial allocation sequence from the National Cancer Institute's Clinical Trial Randomization Tool service (<https://ctrandomization.cancer.gov/tool/>) at recruitment. Study staff not involved in analysis will refer to an externally generated allocation sequence for intervention or comparison allocation. To avoid or limit randomization errors, the crosswalk file and the binary indicator for allocation arm will be known /available to study staff but not investigators involved in analysis or interpretation (until analyses are complete).

This study will include multiple primary care clinic sites in the sense that recruitment will occur at a health-system level in collaboration with Fairview research/trial support and therefore eligible patients can come from many clinics. However, recruitment, consent, pre-screening, data collection, and trial intervention itself are all remote— they do not occur in a clinical site.

Our planned analyses, also discussed in section 9, include an interim analysis approximately five to six months after the beginning of recruitment and data collection to provide preliminary data and feasibility/design information for a later Phase II SBIR application to NIH. This analysis will include all planned endpoints.

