### 10.3 POPULATIONS FOR ANALYSES

Study population will include only intention-to-treat (as randomized).

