## 11.2 DATA HANDLING AND RECORD KEEPING

### 11.2.1 DATA COLLECTION AND MANAGEMENT RESPONSIBILITIES

Data collection will be the responsibility of the study staff under the supervision of the principal investigators. The investigators will be responsible for ensuring the accuracy, completeness, legibility, and timeliness of the data reported.

All source documents will be completed electronically with timestamped activity. End-user data generated in GogyUp Reader will be stored internally by GogyUp by study id and merged with other participant data for exploratory analysis of “adherence” and literacy. Data recorded in the electronic case report form (eCRF) derived from source documents will be consistent with the data recorded on the source documents.

Source document data will be exported from JotForm HIPAA compliant webforms via CSV and be entered into REDCap, a 21 CFR Part 11-compliant data capture system available to the study team through the University of Minnesota’s Clinical and Translational Sciences Institute. The data system includes password protection and internal quality checks, such as automatic range checks, to identify data that appear inconsistent, incomplete, or inaccurate. Clinical data will be entered directly from the source documents.

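### Because 7.3 decodes the interim arms for the investigators, masking of the final analysis cannot be assured as written

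*Combined protocol and SAP*

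**What the plan says.** Two places promise that arm identity stays hidden until the end. Section 5.1.3 makes the crosswalk and the binary arm indicator available "to study staff but not investigators involved in analysis or interpretation (until analyses are complete". Section 7.3 makes unblinding conditional on every participant having had the final visit and on the masked comparative analyses being finished.

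For the interim, at about five to six months, 7.3 provides that for participants recruited in the first three months "an additional study id variable (interim study id) and REDCap trial arm indicator (interim indicator) will be used", and says that "these will ensure that the interim analysis (see above) does not effectively unblind the full analysis". It then says that after the interim "study staff will use the encrypted file to inform the investigators which random study arm number indicated which study arm".

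The investigators "only have access to the REDCap file prior to analysis". On the contents of that file, 7.3 says: "Study staff will then enter name, contact information, study id and baseline variables into REDCap". Section 11.2.1 adds, for the assessment forms: "Source document data will be exported from JotForm HIPAA compliant webforms via CSV and be entered into REDCap". Section 11.1.6, by contrast, says the research data used for statistical analysis carry a study number and no contact or identifying information.

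On the final analysis set, 10.3 says: "Study population will include only intention-to-treat (as randomized". Nothing excludes the interim participants.

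**The concern.** The interim decoding conflicts with both promises for the interim participants. The only safeguard offered is a relabelling, and a new id and arm code do not change the records under them. People who have been told the interim arms, and who later work on a file holding the same participants, have what they need to read the final code.

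At stake is a stated property of the trial. A report relying on 7.3 would describe the final analysis as masked, although the procedure cannot guarantee it. Some choices are still open after the interim, and they could then be made by people who know the arms and the interim result.

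**Working it through.** The plan gives no figure on this point, so there is none to reproduce. The check sets the provisions side by side and adds two illustrations.

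**1. Is arm identity disclosed before the final analysis?** Yes. The interim is at about month 5 to 6 (5.1.3, 10.4.6) of a study of up to 12 months (2.1), and 7.3 has the decoding follow it.

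**2. Do the same participants return?** Yes. The final set is everyone randomized (10.3).

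**3. Is the link between the two files broken?** No provision breaks it. The interim id is described as additional to the ordinary id. The protocol does not say that the interim variables are dropped from the final file, that the interim file is withdrawn, or that a different analyst runs the final analysis. Even if the interim variables were dropped, each participant's baseline scores, age, gender, race and follow-up scores would be the same in both files.

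**4. How many participants overlap?** Assume uniform accrual over A months and total N. The interim participants then number N × 3/A. With N = 160, the target in 10.2:

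| A (months, assumed) | Share 3/A | Participants |
|---|---|---|
| 6 | 50% | 80 |
| 8 | 38% | 60 |
| 9 | 33% | 53 |
| 12 | 25% | 40 |

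If the 12 months must also hold the last three-month follow-up, accrual lasts at most 12 − 3 = 9 months and the overlap is at least about 53.

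**5. Could records be matched without ids or names?** A simulation (500 runs) used the subscale means and SDs in 10.2 (3.85 and 0.74; 2.98 and 0.54). Its assumptions were score steps of 0.2 and 0.25, age about 55 with SD 13, two genders, four race groups, and all variables independent. At N = 160, about 99% of participants were unique on the two baseline scores plus age, gender and race (lowest run 95%). On the two scores alone, about 26% were unique.

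**6. How many matches are needed?** One. A masked comparison of two arms uses a two-level code, so one correctly linked participant of known arm fixes both levels for everyone, including later recruits whose allocation was never disclosed.

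**7. Is there a second route?** Only conditionally. The user-experience questions go to the app arm alone (15.8, 15.8.2, 15.9.6) and are recorded in the online form. If they are exported with the other JotForm data into the file the analysts use, a filled field shows the arm without any use of the interim. Section 11.2.1 suggests this but does not say it of the analysis file.

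**The case against.** The separate interim id and indicator are a real safeguard. The final key stays encrypted until the final analyses are done, and decoding would take a deliberate match. The documents do not say whether the final extract keeps the interim variables. A reader might infer that the final analysis will in fact be unmasked, but the text does not show that. It shows only that the blind would rest on investigators choosing not to link records, which is less than 7.3 claims.

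The consequence is also limited. The primary model is a prespecified ANCOVA with baseline as covariate, and attrition is handled by last observation carried forward (10.4.2). Pattern-mixture values enter sensitivity analyses only. Investigators have no contact with participants, and the staff who collect outcomes are unblinded in any case. All of this stands.

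Three stronger readings are tempting and are not supported:

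- A reader might infer that the decoding inflates type I error through the choice of when to stop enrolling. Section 10.4.6 says the interim will not prompt discontinuation. Section 10.2 sets a target of 80 per arm, calls 60 a low estimate, and gives 200 as attempted recruitment allowing for failures. Tests are two-sided (10.4.1), so an interim p-value is the same whichever label is the app, and decoding the arms does not change it.
- A reader might infer that the user-experience items certainly reveal the arm. The list of REDCap entries in 7.3 does not include them, and 15.9 describes them as information for the app's developers.
- A reader might infer that analysts will work with names. Section 7.3 puts names into REDCap, but 11.1.6 excludes identifiers from analysis data. The two sections conflict, and the point does not depend on which is followed.

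**Conclusion.** The point holds in this form: 7.3 claims to ensure that the interim does not unblind the full analysis, and the procedure it describes cannot ensure that. This follows from the text alone, namely decoding after the interim, reuse of the same participants, and no provision that separates the files or the analysts.

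The overlap of 40 to 80 of 160 rests on assumed uniform accrual over 6 to 12 months. The 99% uniqueness rests on assumed distributions. Neither figure is critical, since a single match is enough.

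The exposure lies in the decisions left open:

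- the pattern-mixture values, which 10.4.2 limits only to plausible ones;
- late follow-up, where the schema allows Day 90 ± 15 but 2.1 and 5.1.3 allow an extra month;
- replaced participants, where 8.2 bars replacement after the intervention has been received but 15.8.3 provides for it after a missed follow-up;
- interpretation of the results.

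This should be corrected before the interim. It does not undermine the primary model.

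**What to change.** Choose one of two routes in 7.3.

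- **Keep the final analysis masked.** Let the study staff who already hold the key label the interim tables for the SBIR application, and withhold arm identity, including those labelled tables, from whoever runs the final analysis.
- **Allow investigators to see labelled interim results.** Delete the claim that the second id ensures masking, state that the final analysis is not masked, and lock the final analysis code and pattern-mixture values before the interim.

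In either case, give the analysts an export limited to id, masked arm, outcomes and baseline covariates, without the interim variables or the user-experience items. Reconcile 7.3 (names entered in REDCap) with 11.1.6 (no identifiers in analysis data).

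The cost is protocol wording and REDCap access rights. The downside is small: the investigators who run the final analysis wait for decoded results, or the report says plainly that the final analysis was not masked.
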